Surgical service lines will include orthopedic total joint, orthopedic spine, gynecology/oncology, thoracic, general, hernia, colorectal, open vascular, plastic, and open urological procedures. These lines will be randomized 1:1 to either the bundle of activities or usual care. The unit of randomization is the service line. The perioperative environment (the patient, the patient to follow, and all providers caring for the patient and the patient to follow) for the randomized service line (treatment or usual care) will be involved in surveillance. This means that all patients, all providers caring for those patients (changes day by day), and care environments (equipment and stopcock sets) will be involved in surveillance. Surveillance from treatment and control groups will yield *S. aureus* transmission events that will be processed to guide proactive improvements in the treatment bundle.

Treatment group (bundle) inclusion/exclusion criteria:

Inclusion criteria: Patients seen at UIHC who are scheduled to undergo surgery from providers in one of the service lines above, documentation of informed, written consent, >18 years of age, procedure requiring general/regional anesthesia.

Exclusion criteria: Lack of documented informed, written consent, patients <18 years of age, procedures outside of the surgical service lines listed above, not requiring general/regional anesthesia, patients not seen in the UIHC clinics, and an allergy to iodine/shellfish or chlorhexidine.

Usual care group (existing practice at UIHC) inclusion/exclusion criteria:

Inclusion criteria: Patients seen at UIHC who are scheduled to undergo surgery from providers in one of the service lines above, documentation of informed, written consent, >18 years of age, procedure requiring general/regional anesthesia.

Exclusion criteria: Lack of documented informed, written consent, patients <18 years of age, procedures outside of the surgical service lines listed above, not requiring general/regional anesthesia, patients not seen at UIHC, and an allergy to iodine/shellfish or chlorhexidine.

VI.14

Provide an estimate of the total number of subjects that would be eligible for inclusion in each of your study populations (include your control population if applicable)

We anticipate that >80% of all patients undergoing surgery in the surgical service lines above will be eligible for the study.

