- *Procedures include a confederate pretending to be another participant in the study.*
- *Participants will be told that the research includes completion of a particular task, when in fact, that task will not be administered.*
- *Study is designed to introduce a new procedure (or task) that participants are not initially told about.*
- *If yes, a waiver of informed consent must be requested under question IV.3.*

No

VII.E. Project Description (E)

VII.E.1 *Will subjects be randomized?*

Yes

VII.E.1.a *Will any subjects be blinded to which study arm they have been assigned?*

Yes

VII.E.1.b *Does the protocol permit telling subjects their treatment assignment at the end of the entire study?*

No

VII.E.1.d *Justify why subjects cannot be told what study arm they have been assigned. You will need to disclose to subjects in the consent document that they cannot receive this information.*

This is a quality improvement project protected by quality assurance.

VII.E.2 *Describe randomization scheme/assignment including ratio such as 1:1, 2:1 etc.*

The service lines have been previously described. These lines will be randomized 1:1 to treatment (bundle) and usual care. This randomization will be computer generated by RDB software.

VII.E.3 *Will any questionnaires, surveys, or written assessments be used to obtain data directly from subjects in this study?*

No

VII.E.5 *Does this project involve creating any audiotapes, videotapes, or photographs?*

No

VII.E.6 *Provide a detailed description in sequential order of the study procedures following the consent process - DO NOT cut and paste from the Consent Document.*

Describe study populations separately if they will be participating in different procedures - include CONTROL population if applicable.

DESCRIBE:

- *What subjects will be asked to do/what happens in the study (in sequential order)*
- *The time period over which procedures will occur*
- *The time commitment for the subject for individual visits/procedures*
- *Long-term followup and how it occurs*

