 - Improved environmental cleaning: Environments (OR and ward) affected by high-risk S. aureus transmission events will be mapped by surveillance and addressed by automated reporting to the anesthesia workroom supervisor. This will trigger improvements in routine (standard cleaning using quaternary ammonium compound and micro cloth followed by a surface disinfection wipe) and terminal [improved routine technique followed by employment of robotic cleaning (Ultraviolet light)] cleaning.
- Fatigue mitigation: The team will use surveillance to continually monitor the impact and fatigue of the proposed interventions as conveyed by failure mode analysis of transmission dynamics involved clonal S. aureus transmission.

XI.2

Provide the rationale or power analysis to support the number of subjects proposed to complete this study.

Statistical Analysis: The unadjusted primary intention to treat analysis will compare the proportion of clonally-related S. aureus transmission events occurring in treatment vs. control perioperative (preoperative, intraoperative case pair, and postoperative) observational units across the 6 randomized service lines using the Chi squared test. We will assess for balance for variables known to be associated with intraoperative

transmission (case, duration > 2 hours, and discharge location). In the case of imbalance, we will use multivariate techniques to further explore the treatment effect using a generalized linear models approach.

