Initial Power Analysis (see amendment below based on reviewer concerns): We intend to screen a total of 1000 patients for up to 10 surgical service lines. Service lines will be randomized 1:1, yielding 500 patients in each treatment arm. Each patient will provide 4 observational units that include preoperative to intraoperative, intraoperative case 1 to intraoperative case 2, intraoperative case 1 to postoperative, and preoperative to postoperative opportunities for detection of *S. aureus* transmission. Thus, 500 patients in each arm will provide 2,000 observational units for a total of 4,000 observational units during the two-year study period. We originally calculated that this provided 90% power to detect a 30% relative reduction in the primary outcome (10.58% down to 7.41%). The estimated clonally related *S. aureus* transmission rate was based on a previously reported detection rate of 58 events in 548 observational units for all-comers to the operating room at 3 major academic medical centers in the United States. To address service line variation, we supposed that the logit-frequencies of the primary outcome for each service line were distributed as a normal distribution with a mean of -0.41 and standard deviation of 0.20. This amount of between-line variation corresponds to an intra-cluster correlation (ICC) of approximately 1%. It can also be interpreted as the amount of variation in which service lines in the top quartile of rates would have an average frequency (after removing within subsection binomial variation) of 46% while service lines in the lowest quartile have an average frequency of 33%. These calculations were accomplished using Monte Carlo simulations written in R 3.3, and using in part the following approximation for the ICC when rates are logit-normal, $1/(1+1/\sigma^2 \cdot \pi^2 \cdot \text{pa}(1-\text{pa}))$ (which can be readily derived using the delta theorem) where pa is the average frequency across centers and σ^2 is the standard deviation on the logit scale. We calculated that this provides 85% power to detect a 30% relative reduction in the primary outcome (40% down to 28%) if there is significant variation between service lines. If indeed there is no variation between service lines, the power is 98%.

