We expect to lose some patients that are consented and enrolled in this study to non-compliance with study protocol. There may also be instances where the first OR case consented to the study but the following OR case does not consent on the day of surgery, making it an ineffective pairing for the study. Patients may also consent to the study when in the surgical clinic but change their mind and not consent to the study on the day of their operation. It is the patient's right to be able to exit the study at any time. In anticipation of patients who are consented but are not able to be used in the study we will need to consent more than the minimum 2000 total patients to reach the needed power. We estimate that consenting 2800 patients will give us enough room after drop-out/ineligibility due to a number of causes to generate a final amount of 2000 (as detailed above) successful patients that generate data for our study.

We have completed a pilot study at UIHC to evaluate the above power analyses. The pilot involved bacterial surveillance in approximately 40 observational units, or 80 cases. A total of 81 cases were enrolled because there was an unexpected cancellation. The primary outcome was intraoperative *S. aureus* transmission events. For the pilot, transmission events were defined as possible epidemiologically-related events, not yet clonal-additional testing required.

Below is a summary of the case-pairs observed stratified by service line.

Case Type # of Cases
Colorectal 10
Cardiothoracic 2
Gyn/onc 24

Orthopedics 44
Vascular 2
Total Cases 81

As orthopedic and gyn/onc procedures represented the majority of randomized units, we considered that those cases would serve as the best estimates for service line variation in *S. aureus* transmission detection. The incidence of *S. aureus* transmission detection ranged from 28% (orthopedic cases) to 58% (gyn/onc) cases. These results support our prior assumptions of anticipated service line variation, power calculations, and study design, and the variation is likely to be less with additional genomic analysis. Our hope is that this additional work and discussion can alleviate the reviewer concerns regarding study design.

XII. Future Research

- XII.1** *Do you wish to keep any information about subjects involved with this research project so that members of the current research team may contact them in the future for your own research projects?*
No

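### A handful of service lines is allocated once, 1:1, with no stratification or constraint; a chance imbalance between lines, such as both orthopedic lines in one arm, passes straight into the unadjusted primary comparison.

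*Protocol*

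**What the plan says.** Protocol VI.13 states: "The unit of randomization is the service line". It lists ten lines, two of them orthopedic: "Surgical service lines will include orthopedic total joint, orthopedic spine, gynecology/oncology, thoracic, general, hernia, colorectal, open vascular, plastic, and open urological procedures". The whole allocation scheme is in VII.E.2: "These lines will be randomized 1:1 to treatment (bundle) and usual care", followed by "This randomization will be computer generated by RDB software". No strata, matching or balance criterion is given there or elsewhere.

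The number of lines is not settled. VI.13 lists ten, VII.D.2 lists nine under partly different names, the analysis text in XI.2 refers to six, and the power text says "We intend to screen a total of 1000 patients for up to 10 surgical service lines".

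Under XI.1, treatment lines get the bundle and usual care lines do not, throughout the two years. No run-in phase or change of arm is described. The SAP's comparison before and after surveillance feedback is confined to the treatment group.

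The protocol expects lines to differ. The power text in XI.2 assumes a between-line SD of 0.20 on the logit scale, and the pilot's detection rate "ranged from 28% (orthopedic cases) to 58% (gyn/onc) cases". The protocol's primary test is an unadjusted chi-squared test. XI.2 adds a balance check on "variables known to be associated with intraoperative" transmission (case, duration over 2 hours, discharge location), with generalized linear models if imbalance is found. The SAP repeats its Poisson model with clustering by surgeon or specialty.

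**The concern.** With six to ten units and one draw, 1:1 allocation controls how many lines each arm receives but not which ones. Two lines belong to the same broad specialty, and the pilot suggests that this specialty sits at the low end of the range. If both fall in one arm and a high-rate line falls in the other, the arms start apart. The unadjusted test then reads that gap as bundle effect or, in the opposite draw, loses a real effect in it. Later adjustment has little to work with when a type of surgery occurs in one arm only.

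**Working it through.** **Inputs.** Ten lines, two orthopedic (VI.13); 500 pairs per arm (XI.1); target 40% to 28%, i.e. 12 points, logit mean -0.41 and SD 0.20, and pilot rates of 28% and 58% (all XI.2). Assumptions not in the documents: 28% applies to both orthopedic lines, 40% to the seven lines other than orthopedics and gyn/onc, and lines have equal size.

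**The plan's own figures.** A two-sided 5% test of 40% v 28% with 500 per arm has power 98.0%, as stated for no line variation. The intra-cluster correlation is 1/(1 + 1/(0.20² × 0.40 × 0.60)) = 0.95%, matching the stated 1%.

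**Probability that both orthopedic lines share an arm.**
- Ten lines, 5:5: 2 × C(8,3)/C(10,5) = 112/252 = 44.4%.
- Nine lines, 5:4: also 44.4%.
- Six lines, 3:3, two of them orthopedic: 2 × C(4,1)/C(6,3) = 8/20 = 40%.
- Independent coin flips with no forced split: 50%.

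**Gap between arms before any bundle effect (ten lines, 5:5).**

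| Allocation | Draws of 252 | Arm means (%) | Gap (points) |
|---|---|---|---|
| Orthopedics together, gyn/onc opposite | 2 × C(7,3) = 70 (28%) | (28+28+3×40)/5 = 35.2; (58+4×40)/5 = 43.6 | 8.4 |
| Orthopedics together with gyn/onc | 2 × C(7,2) = 42 (17%) | (28+28+58+2×40)/5 = 38.8; 40.0 | 1.2 |
| Orthopedics split | 140 (56%) | (28+58+3×40)/5 = 41.2; (28+4×40)/5 = 37.6 | 3.6 |

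With every non-orthopedic line at 40%, putting the orthopedic lines together gives 2/5 × (40 − 28) = 4.8 points, 40% of the target. Reaching 6 points at equal weights needs the other lines to average 43%: 2/5 × (43 − 28) = 6.0. If lines contribute in proportion to pilot case numbers, orthopedics is about 70% of its arm, and the shift with the others at 40% is 0.70 × 12 = 8.4 points.

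**Effect on the chi-squared test**, each pair counted as one observation and line rates fixed as in the table:
- No bundle effect, 8.4-point draw: standard error √(0.394 × 0.606 × 2/500) = 3.09 points, z = 2.72, so P < .05 about 78% of the time, in the direction chance dictates. With orthopedics split: z = 3.6/3.09 = 1.17, about 21%.
- True 30% reduction, gyn/onc treated and orthopedics in control: 35.2% v 0.7 × 43.6 = 30.5%, power about 35%. Worst case with orthopedics split: 37.6% v 0.7 × 41.2 = 28.8%, about 84%.

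**Under the protocol's own variation.** A logit SD of 0.20 at 40% is about 0.40 × 0.60 × 0.20 = 4.8 points per line. The chance difference between arms has SD 4.8 × √(2/5) = 3.0 points with ten lines and 4.8 × √(2/3) = 3.9 with six. By simulation, a gap of 6 points or more occurs in 4.6% and 12.3% of allocations. At that SD the type I error of the unadjusted chi-squared test is 15.6% (ten lines) or 22% (six); a line-level t test holds about 5%.

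**The case against.** Any parallel cluster trial lacks a within-line contrast. Randomization balances lines in expectation, and an analysis that treats lines as the units carries the chance imbalance in its standard error. A reader might infer that line differences and the bundle cannot be told apart at all; that goes too far. What stands is that the protocol's chi-squared test carries no such allowance, and that the SAP's multilevel repeat widens the uncertainty without removing an imbalance that has occurred.

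A reader might also take the 44% as the chance of a shift of half the target or more. It is not. In the example that happens in 28% of draws and needs gyn/onc in the opposite arm; in 42 of the 112 draws with orthopedics together, the gap is only 1.2 points, smaller than the 3.6 that splitting them gives. Nor is the allocation wholly unrestricted: the 44% presupposes a forced 5:5 split.

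The pilot rates are weak evidence. They count possible events before clonal testing, whereas the primary comparison is of clonally related events, and XI.2 itself expects less variation after genomic analysis. If they reflect about 12/44 and 14/24 cases (counts not given), the 95% intervals are 16–42% and 39–76%; by pairs, 6/22 v 7/12, Fisher P = 0.14. No separate rates are given for total joint and spine. All of this stands and limits the size of the point.

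The planned balance check and model adjustment help with duration and discharge location. They cannot replace overlap in type of surgery.

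**Conclusion.** The point holds as an inexpensive design improvement, not as a fatal flaw. A single draw of six to ten lines with nothing beyond 1:1 leaves a 40–44% chance that both orthopedic lines share an arm (given two orthopedic lines and an even, or 5:4, split). On the illustrative rates the starting gap is 8.4 points, 70% of the 12-point target, in 28% of draws. On the protocol's own SD, a gap of half the target is uncommon: about 5% with ten lines, 12% with six. The documents do not settle which picture is closer to the truth for clonal events. In either case the primary test does not allow for the imbalance.

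**What to change.** First settle the number and names of the lines, so that VI.13, VII.D.2 and XI.2 agree. Then, in VII.E.2, replace the plain 1:1 draw with stratified or constrained randomization that at least puts the two orthopedic lines in opposite arms. With ten lines, 140 of 252 allocations remain and the worst gap in the example falls from 8.4 to 3.6 points. Optionally, also balance on historical case volume, share of cases over 2 hours and discharge location, with tolerances stated beforehand and the number of remaining allocations reported. Account for the constraint variables in a line-level or clustered analysis.

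The cost is a short randomization script before the single allocation and, for the optional part, one historical hospital report. The downside is fewer permissible allocations. With ten lines this is minor: the smallest two-sided permutation P value goes from 2/252 = 0.008 to 2/140 = 0.014. With six lines only 12 of 20 allocations remain and the smallest P value is 2/12 = 0.17 (2/20 = 0.10 unconstrained), so a permutation test would be too coarse and a model-based clustered analysis would be needed. A line-level analysis also has a price in power: in simulation at SD 0.20 without the constraint, a line-level t test reaches about 73% with ten lines and 49% with six, below the stated 85%.

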Preoperative swab kit orders will track informed, written consent and will populate a list in EPIC for the PI ([name]) that will be sorted by type of surgery and filtered (at the top of the list) by patients with orders for the kit that are actually booked for surgery within 10 days of the current date. That list will be used by [name] to send kits to patients for preoperative swabbing and if in the treatment group, decolonization with Povidone iodine. Before sending, a new signed and held POC preoperative swab kit order will be placed and associated with the kit number. The kits will be sent by the research team to the patient along with a prepaid mailer. The kit will include 3 swabs (nasal, axillary, and groin), preprinted instructions for use, and an insert briefly summarizing the study for a reminder (see attached documents). The patient will follow the kit instructions and send the kit to RDB for processing.

RDB will process the samples and enter the results into the software platform. RDB will send a list of kit numbers received to [name]. [name] will complete the signed and held order in EPIC for those received. This will create an ICON indicating complete. The complete ICON will guide OR PathTrac Surveillance, where a treatment and control patient are selected each day, as geographically dispersed as possible in the OR.

Patients in treatment lines with completed orders who are selected for surveillance will receive the treatment bundle (see below). Patients in usual care lines with completed orders who are selected for surveillance will receive usual care. All second patients in the observational pairs described below will receive usual care. Only the first patient in a treatment pair will receive the bundle (The goal is to examine the impact of an evidence-based bundle in preventing spread of bacteria from one patient to another).

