Reducing Perioperative S. aureus Transmission via use of an Evidence-Based, Multimodal Program Driven by an Innovative Software Platform (OR PathTrac)

9/20/2018

Statistical Analysis

Multiple statistical methods were used. For simplification, we list the statistical methods in the precise sequence they are reported in the results.

The Fisher exact test was used to compare patient and procedural demographic information for treatment vs control groups and for cases involving *S* aureus transmission. Similarly, the distribution of patients by ASA scores greater than 2 and by sex for enrolled vs eligible patients were compared by surgeon using the Mantel-Haenszel test.

The Fisher exact test was also used to examine the potential association of each of the covariates mentioned earlier with *S aureus* transmission. None were associated.

A 2-sided Wilcoxon-Mann-Whitney test was used to examine the association of treatment assignment with the number of transmitted *S aureus* isolates. Poisson regression was used to estimate the incidence risk ratio (IRR) of *S aureus* transmission for the independent variable of treatment. Poisson regression was used to estimate the IRR because the incidence of transmission was so large (ie, much greater than 10%) that the odds ratio estimated using logistic regression would be a biased estimator of the relative risk.²⁴ We repeated the analysis using multilevel Poisson regression clustering by surgeon or specialty.

The Fisher exact test was used to compare the proportion of patients in the treatment group with transmission events before vs after surveillance feedback and the proportion of patients with SSI with and without documented *S aureus* transmission. Poisson regression was used to compare the proportion of patients with SSI with and without documented *S aureus* transmission, clustered by surgeon.

The proportion of patients with SSIs was compared with the Fisher exact test. Time to infection was evaluated by Cox proportional hazard modeling. We repeated the analysis using multilevel Poisson regression clustering by surgeon and specialty.

There were no missing data for the primary and secondary outcomes. Calculations were performed using Stata version 16.1 (StataCorp). All P values were 2-sided, and P < .05 was taken to indicate statistical significance.

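### The daily selection rule sets no number of pairs per service line; if line sizes are as uneven as the pilot suggests, a cluster-adjusted comparison loses roughly 4 to 16 points of power

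*Protocol*

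**What the plan says.** Protocol VI.13 lists ten surgical service lines and makes the line the unit of randomisation. Under VI.15 and VII.D.29, research assistants work a list of patients with completed kit orders and choose two each day, one per arm. VII.E.6 adds that "a treatment and control patient are selected each day, as geographically dispersed as possible in the OR". XI.1 calls the observed patient randomly selected and fixes the total at 500 case pairs per arm. None of these sections says how the 500 are to be divided among the lines of an arm.

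VI.14 says that the number of patients per line is not known and applies one figure, about 1200 eligible, to every line.

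XI.2 describes up to ten lines: "Service lines will be randomized 1:1, yielding 500 patients in each treatment arm". Line rates are assumed normal on the logit scale with a "mean of -0.41 and standard deviation of 0.20". The sample size then "provides 85% power to detect a 30% relative reduction in the primary outcome (40% down to 28"%), and "If indeed there is no variation between service lines, the power is 98"%. No line sizes are given for that simulation. The opening paragraph of XI.2 names six randomised lines and an unadjusted chi-squared test. The pilot in XI.2 lists 44 orthopedic, 24 gyn/onc, 10 colorectal, 2 cardiothoracic and 2 vascular cases, and comments: "As orthopedic and gyn/onc procedures represented the majority of randomized units".

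The SAP repeats its Poisson analysis as a multilevel model clustering by surgeon or specialty, and states: "All P values were 2-sided, and P < .05 was taken to indicate statistical significance".

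**The concern.** With randomisation by line, each arm's result carries the transmission rates of the few lines assigned to it. Further pairs from a busy line reduce the binomial error but not that line's own deviation. If two or three lines supply most of an arm's 500 pairs, the arm holds less information than five evenly sampled lines would give, although the recruitment target is met in full.

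Nothing in the selection rule prevents this. Geographic dispersion spreads the two daily observations across the operating rooms, and random choice among patients with returned kits reproduces the case mix. Either way a line's share tends to follow its supply of consented patients. The stated power contains no visible allowance for unequal lines.

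**Working it through.** **Inputs.** From XI.2: 40% v 28%, 500 pairs per arm, logit SD 0.20, ten lines (five per arm). From the SAP: two-sided 5%. The between-line SD is treated as known. A test that had to estimate it from ten lines would have lower power throughout, including for equal lines.

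**Formula.** On the proportion scale the between-line SD is about 0.20 x p(1-p): 0.20 x 0.24 = 0.048 at 40%, and 0.20 x 0.2016 = 0.0403 at 28%. With w the share of an arm's pairs that comes from each line,

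Var(difference) = 0.24/500 + 0.2016/500 + (0.048² + 0.0403²) x Σw² = 0.000883 + 0.00393 x Σw².

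For k lines per arm, Σw² = (1 + CV²)/k. Power = Φ(0.12/SE - 1.96).

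**The plan's own figures.**
- No line variation: SE = 0.0297, z = 4.04, power 98.1% (stated 98%).
- Five equal lines per arm: Σw² = 0.20, SE = 0.0409, z = 2.94, power 83.6% (stated 85%).
- Design-effect route, 1 + (100 - 1) x ICC, reading the printed ICC approximation as 1/(1 + 1/(σ²p(1-p))): ICC = 0.0095, 0.0089 and 0.0080 at p = 0.40, 0.34 and 0.28, giving 82.2%, 83.4% and 85.1%.

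The stated 85% is therefore what near-equal lines give.

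**Unequal lines, same formula.**
- CV 0.2: 83%
- CV 0.4: 81%
- CV 0.5: 79%
- CV 0.8: 73%
- CV 1.0: 68%

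**What CV might apply?** The documents do not say. In the pilot, orthopedics and gyn/onc supply (44 + 24)/82 = 83% of the listed cases. To map the pilot onto the ten lines of VI.13, I assume that orthopedics splits equally into its two lines (22 and 22). The four lines with no pilot entry (general, hernia, plastic, urological) are each given 2, 5, 10 or 15. Results are averaged over all 252 ways of assigning ten lines to two arms of five. Efficient weighting means weighting each line by the inverse of p(1-p)/m + (between-line SD)², where m is the line's number of pairs.

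| Count given to each unseen line | CV over ten lines | Power, pairs weighted equally | Power, efficient weighting |
|---|---|---|---|
| 2 | 1.03 | 68% | 74% |
| 5 | 0.83 | 73% | 78% |
| 10 | 0.62 | 78% | 80% |
| 15 | 0.52 | 79% | 80% |
| All lines equal | 0 | 84% | 84% |

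The loss runs from about 84 - 80 = 4 points to about 84 - 68 = 16 points.

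**Under the unadjusted chi-squared test.** This test ignores the between-line term. With both arms at 40%, it uses a variance of 2 x 0.24/500 = 0.00096, whereas the true variance is 0.00096 + 2 x 0.048² x Σw². True size = 2[1 - Φ(1.96 x √(0.00096/true variance))]:
- equal lines: true variance 0.00188, size 16%;
- CV 0.5: 0.00211, size 19%;
- CV 1.0: 0.00280, size 25%.

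Its nominal power is 93% with equal lines and 89-92% with pilot-like sizes.

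**Six lines.** Three equal lines per arm: Σw² = 1/3, SE = 0.0468, z = 2.56, power 73%.

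**The case against.** A reader might infer that pairs will certainly concentrate in a few lines. The documents do not support that. VI.14 gives no line volumes, and its flat 1200 eligible per line, against about 100 pairs needed, would make balance feasible. The pilot covered about 40 pairs, is not described as using this trial's selection rule, and shows nothing for four of the ten lines. The counts assumed for those four move equal-weight power from 68% to 79% on their own. This stands: concentration is likely, not established, and the range is conditional.

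A reader might also take the full drop from 85% to the high 60s as the cost. That overstates it in two ways. The like-for-like baseline is 82-84%, and an analysis that weights lines efficiently keeps 74-80%. Nor can it be said that 85% requires exactly equal lines, since a CV of 0.2 gives 83%.

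The strongest objection is that under the chi-squared test in XI.2 the trial hardly loses nominal power. That is correct. The damage there is to type I error, and most of it (16% against a nominal 5%) is present with equal lines. Uneven sizes only add to it. The power loss applies to a cluster-adjusted analysis, to which the SAP's multilevel repeat by specialty comes nearest.

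Equal targets also have a cost: they move the estimate from a case-mix average towards a line average, and a visible roster would let staff foresee observed days.

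**Conclusion.** The point holds in conditional form. The plan randomises lines but does not control how many pairs each line supplies, and its 85% power fits ten near-equal lines. If the line-size CV is about 0.5 to 1.0, cluster-adjusted power is about 68-79% with equal weighting of pairs or 74-80% with efficient weighting. At a CV of 0.4 or less the loss is under 3 points. Under the unadjusted test, pilot-like sizes raise type I error from about 16% to 19-25%. These figures rest on the plan's own SD of 0.20, a known between-line variance, ten lines, and assumed counts for the four lines absent from the pilot. The conflict between six lines and up to ten matters as much: six equal lines already give only about 73%. This is a cheap design improvement; it does not show that the trial is bound to be underpowered.

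**What to change.** In VII.E.6 and VII.D.29 (and VI.15, which repeats the rule), select the daily patient in each arm by a rotation over that arm's lines. Set the target at 500 divided by the number of lines in the arm, which is about 100 pairs for five lines. If the scheduled line has no eligible pair that day, take the next line, and keep geographic dispersion as the second criterion. Preferably randomise the order of the rotation and conceal it from operating-room staff.

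In XI.2, first reconcile six lines with up to ten. Then restate the power for a cluster-adjusted analysis over a range of line-size CVs, for example 0 to 1.0, and say how lines of unequal size will be weighted.

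The cost is a roster, a few protocol sentences and a re-run of the existing simulation, with no extra patients. Low-volume lines may miss slots, and the estimate moves towards a line average, so the plan should say which average is intended. The rotation limits the added type I error from uneven lines; only an analysis that accounts for clustering removes the rest.
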